7. DATA ANALYSIS

a. Sample Size

In order to measure national coverage of DSD, we will access data for up to the entire national ART cohort. In Malawi, the estimated number of individuals on ART is currently 740,000 [16]. This is expected to increase to \geq 90% of the entire HIV-infected population by the time the study ends. We therefore expect to collect and analyze data for up to 1,000,000 individuals, the estimated HIV-positive population in Malawi [16]. As noted above, all data will be drawn from records that exist at the time of data collection; the study will have no interaction with study subjects.

b. Outcomes

To estimate uptake, benefits, and costs of DSD, we will aim to report the following results, stratified by model care and/or other patient or clinic/model characteristics:

- Percentage of current ART patients eligible for any alternative model, under current guidelines
- 2. Demographic, economic, and clinical characteristics of patients in each model, as data allow.
- 3. Patient-months enrolled in any DSD and in each model
- 4. Frequency of transfer between models of care, including back to the conventional model
- 5. Location, duration, and frequency of ARV dispensing
- 6. Number of clinical visits/patient/year
- 7. Quantities of resources used/patient/year
- 8. Geographic distribution of patients enrolled in each DSD
- 9. Retention on ART, measured at 6-month intervals
- 10. Proportion virally suppressed (< 400 copies/ml³)
- 11. Other outcomes relevant to DSD that can be estimated from available data

Note: as this is not a clinical trial, we have not designated primary and secondary outcomes. We will report as many of the above outcomes as data allow.

c. Analysis

To evaluate the broad, national- or system-wide implications of differentiated models of ART delivery in the context of health systems in sub-Saharan Africa, we will conduct the following analyses.

Outcomes 1-4 above entail description of the models of care and the patients enrolled in them. For these outcomes, we will begin by categorizing patients in the sample as to whether they are eligible for and receiving one of the models of care and report the proportion in each group. We will then describe the demographic, economic, and clinical characteristics of patients stratified by model of care (age, gender, time on ART, baseline CD4, and others) using means or medians as appropriate for continuous variables and proportions for categorical variables. We will further quantify the number of patientmonths enrolled in any DSD model and in each specific model and the frequency of transfer between models of care, including back to the conventional model. We will look for differences in the models of care, number of patient-months enrolled, and frequency of transfer by demographic, economic, and clinical characteristics using stratified analyses and report risk differences and corresponding 95% confidence intervals. As the analysis is meant to be descriptive we will not conduct regression analyses as our primary analyses.

Outcomes 5-6 describe characteristics of the models of care that are being implemented. Separately from this protocol, we will review governmental and implementing partner SOPs, reports, and manuscripts in order to describe features of the models of care including location, duration, frequency

of ARV dispensing, and the number of clinical visits per patient per year (all non-human subjects research). We will report these using means or medians as appropriate for continuous variables and proportions for categorical variables. We will then compare the expected features to patient data and report the proportion of agreement to determine whether the models of care are being implemented as per SOP. We will present these as proportions with corresponding 95% confidence intervals.

Outcome 7 measures the quantities of resources used per patient per year. For this outcome, we will estimate the quantities of resources used per patient per year enrolled in DSD. We will start with bottom-up costing of the resources utilized per patient served in the clinics as recorded in the data. The quantity of each resource used by each enrolled patient will be estimated and then multiplied by the unit cost for that resource. Unit costs will be calculated from clinic invoices, MOH price lists, government salary scales, and other sources of actual costs incurred. We will use a top-down approach to estimate shared costs (e.g. clinic management) where necessary. These will be reported as means and medians, with standard deviations/IQRs.

Outcome 8 measures the geographic distribution of patients enrolled in each DSD. For this outcome we will calculate the percentage of people enrolled in a differentiated model of ART delivery at the facility level, defined as the number of patients enrolled in differentiated service delivery divided by the number of patients currently accessing ART at a site. This will be estimated through either routine patient-level indicators available from national data sources, or aggregate facility-level information from service delivery partners. We will use heat maps to geographically map the level of DSD model coverage by most granular level of information available (province, district, etc.).

Outcomes 9-11 measure health outcomes by model of care. For these outcomes, we will begin with descriptive analyses of the characteristics of the population stratified by model of care. For each outcome described above, we will conduct a crude analysis comparing the proportion of subjects with the outcome by model of care. Next, we will conduct an analysis for each outcome accounting only for clustering using generalized estimating equations (GEE) with an unstructured correlation matrix and clustering by treatment site. In all cases the outcomes are dichotomous and therefore we will calculate risk differences comparing the intervention to the comparison arms using a linear link function and a binomial distribution. Next, should any imbalances between models of care be detected, we will adjust for those covariates in our GEE model. Finally, we will look for differences in the effects of the models of care by important baseline characteristics (e.g. size of the treatment population, rural vs. urban, province, etc.) using stratified analyses.

d. Dissemination of Findings

The results of this study will be disseminated as widely as possible in the study countries and globally. A full report will be made to local stakeholders and will be circulated widely and posted on our website. We will also develop a short briefing document to send to the Ministry of Health, donor agencies, and other interested organizations, and we will present the results at relevant conferences domestically and internationally. One or more journal manuscripts will be submitted to an appropriate peer-reviewed international journal.

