5. STUDY SITES AND POPULATION

a. Study Sites

The evaluation will be conducted nationally in Malawi. Data collected may pertain to the entire national cohort of ART patients (e.g. Baobab Health NART) or to specific smaller cohorts developed by implementing partners, other researchers, and clinics themselves.

b. Inclusion Criteria

This study aims to measure coverage and outcomes of DSD across Malawi. For this reason, we will include in our study all adults who are accessing care for HIV anywhere in the country. The inclusion criteria are shown below.

Inclusion criteria

- ≥ 15 years old
- Patients accessing care for HIV within the data collection period (January 1, 2014 to February 28, 2021)
- In any HIV transmission risk group (general adults and adolescents, high transmission risk populations)

Exclusion criteria

None

Children younger than 15 are excluded from this study for two reasons. First, they are typically treated in pediatric HIV programs that have different drug regimens, visit schedules, and models of care than do adults. Second, the vast majority of DSD implementation in the focus countries to date has involved only adult and adolescent patients, not children [15].

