6. DATA SOURCES AND MANAGEMENT

a. Data Sources

The MOH and its partners will implement the DSD strategies addressed in this study. This protocol is solely for an evaluation of the coverage and outcomes of the interventions. The study team will have no involvement in providing services nor any interaction with patients. The evaluation will instead rely solely on existing, retrospective national-, facility-, and patient-level records.

Routine data sources to be accessed for this study include:

- Baobab Health National ART (NART) System
- Baobab Health Laboratory Information Management Systems (LIMS)
- Other MOH electronic and paper patient records and registers which capture relevant information related to the care and treatment of patients in any model of ART care and treatment. NART does not currently fully capture model of service delivery, for example, so access to paper files at clinics may be required to build the study database.
- Existing, de-identified data sets from trial, cohort, and observational studies, in collaboration with implementers, technical support partners, and research organizations.

The Ministry of Health will be asked to assure and facilitate access to Baobab Health's NART, LIMS and other routinely collected sources of electronic data.

Data will be collected for all patients in each data set who accessed care for HIV on or after January 1, 2014. The focus countries began large-scale implementation of DSD in 2015 or 2016. Starting in 2014

will thus allow us a pre-intervention period for comparison. Data collection will continue throughout the study period, which ends on February 28, 2021.

b. Data Fields to be Collected

Below (Table 1) we summarize the existing data required for the evaluation. A detailed list of data fields follows this summary.

Table 1. Data sought for evaluation of DSD

Themes	Potential availability and source(s)
Proportion of current ART patients meeting definition	Data from electronic medical records, existing M&E reports, IeDEA
of stable; distribution of reasons for not meeting	and PEPFAR partners, cohorts under observation, facilities
definition	participating in others' studies
Geographic distribution and description of	Reports from existing implementers and technical support
differentiated models in use	partners and MOH
Number (proportion) of patients in each model at time	Data from existing implementers and technical support partners,

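### The protocol names risk differences as the measure for patient-months enrolled, where they are undefined, and for frequency of transfer, where they need a binary definition and common horizon that it does not give

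*Protocol*

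**What the plan says.** Section 7b lists Outcome 3 as "Patient-months enrolled in any DSD and in each model" and Outcome 4 as "Frequency of transfer between models of care, including back to the conventional model". Neither entry has a cut-off, a time horizon or a denominator of time at risk.

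Section 7c (Outcomes 1-4) first says that both quantities will be quantified. It then says that the comparisons will cover "differences in the models of care, number of patient-months enrolled, and frequency of transfer by demographic, economic, and clinical characteristics". The method for all three is given as "using stratified analyses and report risk differences and corresponding 95% confidence intervals". One measure is thus attached to three quantities of different kinds: a category (model of care), an amount of time, and an event frequency. The same paragraph keeps regression out of the primary analyses.

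Elsewhere the protocol is more careful. Outcome 6 is scaled by time, "Number of clinical visits/patient/year"; Outcome 7 is also per patient per year, and Outcome 9 is taken at 6-month intervals. For Outcomes 9-11, section 7c gives its reason for the measure: "In all cases the outcomes are dichotomous and therefore we will calculate risk differences".

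**The concern.** A risk difference is the difference between two probabilities. It needs a yes/no outcome for each patient over a stated period. Months enrolled is not such an outcome. Transfer can be turned into one, but the protocol does not say how or over what period.

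Periods of observation will not be equal. Section 5b includes "Patients accessing care for HIV within the data collection period (January 1, 2014 to February 28, 2021"), so patients can enter and leave at any point. Section 6a adds that "The focus countries began large-scale implementation of DSD in 2015 or 2016", and section 6c says that some data sets are already closed on receipt while others stay open until the study ends. Time on ART, one of the characteristics named in section 7c, is itself likely to be related to length of observation.

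Uptake is a specific aim of the study, and duration of participation is one of the evidence gaps named in the summary and background. A comparison by age, sex or time on ART that mixes behaviour with length of observation could mislead on both.

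**Working it through.** The protocol gives no transfer rate and no figure for these comparisons, so there is nothing to reproduce. The check has two parts.

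**1. Does the measure fit each quantity?**

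| Quantity in the section 7c sentence | Type | Risk difference |
|---|---|---|
| Model of care | In the model or not, at a date | Defined |
| Patient-months enrolled | Person-time | Undefined |
| Frequency of transfer | Event that can recur; no binary form stated | Defined only as any transfer within a common horizon |

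The protocol's own condition for the measure in Outcomes 9-11 is that the outcome be dichotomous. Outcomes 3 and 4 as written do not meet it.

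**2. What could happen if transfer were read as ever transferred?**

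From the document:
- The data window, 1 January 2014 to 28 February 2021, is about 86 months.
- Large-scale DSD began in 2015 or 2016. From 1 January 2015 to the end of the window is about 74 months; from 31 December 2016 it is about 50 months. Time since large-scale roll-out therefore tops out at about 50 to 74 months, not 86.

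Assumed, since the document gives no values: a constant transfer rate, the rate itself, and the mean observation time in each stratum.

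Formula: P(at least one transfer in time t) = 1 − exp(−rate × t).

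*Equal rates, unequal observation.* Rate 0.01 per patient-month in both strata:
- 12 months: 1 − exp(−0.12) = 11.3%
- 36 months: 1 − exp(−0.36) = 30.2%
- Risk difference: 30.2 − 11.3 = 18.9 points. Rate difference: 0.

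*Range.* Equal rates in both strata, with 12 months of observation in one and 24 to 60 in the other:
- Smallest, 0.05 per patient-year, 12 v 24 months: 4.9% v 9.5%, or 4.6 points
- Largest, 0.40 per patient-year, 12 v 60 months: 33.0% v 86.5%, or 53.5 points

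*Unequal rates.* 0.20 per patient-year seen for 12 months against 0.10 seen for 36 months:
- 1 − exp(−0.20) = 18.1%
- 1 − exp(−0.30) = 25.9%
- Risk difference: 18.1 − 25.9 = −7.8 points, although the first stratum has twice the rate. The rate difference is +0.10 per patient-year whatever the follow-up.

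No such calculation applies to patient-months. There is no probability to compute until someone chooses a cut-off, and the protocol has none.

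**The case against.** The strongest reply is that this is one loose phrase in a secondary step of a descriptive analysis. Section 7c first quantifies patient-months and transfers with no risk measure attached, and that reporting is unaffected. The paragraph also allows means or medians when it describes continuous patient characteristics, so an analyst might simply report differences in mean months. Frequency of transfer can be read as the proportion who transfer, for which a risk difference exists. Table 1 in section 6b seeks patient-months over the previous 12 months, which is a fixed window. Horizons and denominators are often left to an analysis plan, and one may exist.

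Much of this stands, and it limits the point. Nothing in the document says that analysts must dichotomise patient-months. The Table 1 window, if used, would limit any distortion from unequal follow-up for that outcome. No figure in the document shows that strata differ threefold in observation time.

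It does not remove the point. The Table 1 window is not carried into Outcome 3 or into section 7c, and even with it, months enrolled is still not a risk. Reading transfer as a proportion leaves it without a common horizon. The issue is also not a detail left for later: section 7c names a measure, and the measure does not fit one item on its list.

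**Conclusion.** The point holds as a mismatch between the stated measure and two of the three quantities it is applied to. For patient-months the risk difference is undefined, and this rests on no assumption. For transfer it is valid only with a binary definition and a common horizon, which the protocol does not state.

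The possible distortion for transfer is illustrated by the 18.9 points above. That figure rests on an assumed constant rate of 1 per 100 patient-months and assumed observation of 12 and 36 months; other assumed values gave 4.6 to 53.5 points.

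A reader might infer that the comparisons will mainly measure length of observation, or that patient-months will be judged over the full 86 months. The document supports neither. Differences could partly reflect observation time, large-scale DSD started only in 2015 or 2016, and Table 1 mentions a 12-month window. Nor are risk differences wrong for the whole sentence: for model membership they are the right choice.

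Severity is moderate. Section 7b designates no primary or secondary outcomes, and section 7c calls this analysis descriptive.

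**What to change.** In section 7c, replace the single measure with one for each quantity, each with a 95% confidence interval:

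- **Model of care:** keep the risk difference, for being in a given model or not at a stated date.
- **Outcome 3:** the difference in mean patient-months per patient over a fixed window, for which Table 1's 12 months would serve, or the difference in the share of observed ART time spent in each model.
- **Outcome 4:** transfers per patient-time at risk, with rate differences or rate ratios; or the risk of any transfer by a fixed time after enrolment in a model, in which case the risk difference can stay.

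The cost is a sentence or two of text. None of these needs regression, so the descriptive character of the analysis is kept. They use the enrolment durations and participation dates that section 6b already seeks. Those will not be available everywhere: section 6a notes that the national electronic system does not yet record the model of care in full.

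### Site clustering is planned only for Outcomes 9-11, so the 95% intervals for SOP agreement (Outcomes 5-6) and for between-clinic contrasts (Outcomes 1-4) could be materially too narrow

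*Protocol*

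**What the plan says.** All of this is in protocol section 7c unless noted.

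- **Outcomes 1-4.** Patients are classed by whether they are "eligible for and receiving one of the models of care and report the proportion in each group". Differences by demographic, economic and clinical characteristics are then examined "using stratified analyses and report risk differences and corresponding 95% confidence intervals". The paragraph ends: "As the analysis is meant to be descriptive we will not conduct regression analyses as our primary analyses".
- **Outcomes 5-6.** Patient data on dispensing and visits are compared with what the SOPs lead one to expect, and the share in agreement is reported: "We will present these as proportions with corresponding 95% confidence intervals".
- **Outcome 8.** Here "we will calculate the percentage of people enrolled in a differentiated model of ART delivery at the facility level", shown on heat maps, with no interval.
- **Outcomes 9-11.** After a crude comparison there is a separate step "accounting only for clustering using generalized estimating equations (GEE) with an unstructured correlation matrix and clustering by treatment site".

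On the data, section 7a allows for up to the whole national cohort, where "the estimated number of individuals on ART is currently 740,000". Section 5a also allows smaller cohorts held by partners, researchers or clinics. Section 6a says that the national electronic system does not fully record the model of care, so clinic paper files may be needed. Table 1 plans a quality check at a sample of sites. No variance method for Outcomes 1-6, ICC, number of sites or cluster size is given.

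**The concern.** The authors recognise that patients of one site are correlated, and they handle it for retention and viral suppression. The outcomes left without that step are likely to cluster at least as strongly. Dispensing location, duration and frequency are plausibly shared by most patients of a clinic, and section 3a itself lists setting and clinic capacity among the criteria for allocating models. Section 7b adds that results may be stratified by clinic or model characteristics.

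A patient-level binomial interval around SOP agreement would then reflect the number of patients, although much of the information lies in the number of clinics. The findings go to the Ministry of Health and donors (section 7d). Intervals that are too tight could present chance variation in which clinics were captured as firm knowledge of how faithfully models are delivered.

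**Working it through.** **Inputs.** From the protocol: 740,000 patients on ART; 95% intervals; site as the clustering unit for Outcomes 9-11. Assumed, because not stated: number of sites K, ICC, a smaller cohort of 10,000 patients, equal cluster sizes, and a true proportion of 0.5. The protocol contains no precision calculation, so there is no figure of its own to reproduce.

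**Step 1: naive half-width.** 1.96 × √(0.25/N).
- N = 740,000: 0.114 percentage points.
- N = 10,000: 0.98 percentage points.

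**Step 2: inflation for a single proportion such as SOP agreement.** Design effect = 1 + (m − 1) × ICC, with m = N/K. Its square root is the ratio of correct to naive width, when the observed clinics are treated as a sample from many. Coverage of the naive interval is 2Φ(1.96/ratio) − 1.

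| N | K | m | ICC | Design effect | Ratio | Correct half-width (points) | Naive coverage |
|---|---|---|---|---|---|---|---|
| 10,000 | 300 | 33.3 | 0.01 | 1.32 | 1.15 | 1.13 | 91% |
| 10,000 | 50 | 200 | 0.05 | 10.95 | 3.31 | 3.24 | 45% |
| 740,000 | 1,000 | 740 | 0.01 | 8.39 | 2.90 | 0.33 | 50% |
| 740,000 | 300 | 2,467 | 0.10 | 247.6 | 15.7 | 1.79 | 10% |

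At ICC 0.001, the 740,000 rows would give ratios of only 1.3 (1,000 sites) to 1.9 (300 sites).

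**Step 3: risk differences.** What matters is where the stratifying characteristic varies. A beta-binomial simulation (300 sites of 500 patients, ICC 0.05, 600 runs) gave:
- characteristic balanced within clinics: true/naive standard error 0.94, naive coverage 95%. Theory gives √(1 − 0.05) = 0.97, so the naive interval is, if anything, slightly wide;
- characteristic fixed at clinic level: ratio 5.3, naive coverage 28%. Theory gives √(1 + 499 × 0.05) = 5.1.

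**Step 4: effect of capturing most clinics.** If the target is the finite national cohort and a fraction f of clinics is captured, the ratio is multiplied by √(1 − f). With m = 1,000 and ICC 0.05 it starts at 7.1 and falls to 5.0 at f = 0.5, 2.3 at f = 0.9, 0.7 at f = 0.99 and 0 at f = 1.

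**The case against.** The strongest case against has four parts.

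1. *The protocol is silent; it does not assume independence.* This is true. Stratified risk differences and proportions are compatible with a robust variance, the regression sentence only rules regression out as the primary analysis, and a variance estimator is often left to the SAP. A reader who infers that the protocol states independence goes too far. But the protocol itself assigns a clustering step to some outcomes and not to others, and someone following it as written would produce patient-level intervals.

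2. *Some of the intervals do not exist.* This stands. A reader might infer that eligibility and coverage intervals will also be too narrow. The overall eligibility and receipt proportions are reported without intervals, and facility coverage is Outcome 8, again without one.

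3. *The national data are a census.* This stands in part. With full enumeration and a finite target, clustering adds no sampling error, and the national-scale factors do not apply. But the cohort is only an upper limit on the data, and model of care may be known only for clinics or cohorts that supply it. The protocol also does not name the population to which its intervals refer.

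4. *The planned contrasts are by patient characteristics.* This stands for those balanced within clinics, such as sex in many settings. Characteristics that differ mainly between clinics remain affected.

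**Conclusion.** The point holds in a limited form. Section 7c promises 95% intervals for SOP agreement and for stratified risk differences without the site-clustering step that it requires for Outcomes 9-11. SOP agreement is the clearest case.

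The intervals could be about 1.2 to 3.3 times too narrow in an assumed 10,000-patient cohort (50-300 sites, ICC 0.01-0.05). At national scale the factor is about 3 to 16 (300-1,000 sites, ICC 0.01-0.10), but only if inference reaches beyond the observed cohort to a superpopulation. These are scenarios: a reader might infer that the intervals *will* be several-fold too narrow, but without an ICC or a site count that cannot be derived.

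The analysis is descriptive, no primary outcome is designated, and the health-outcome comparisons already allow for site. It is therefore something that should be fixed, and it does not undermine the study as a whole.

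**What to change.** Add to the Outcomes 1-4 and 5-6 paragraphs of section 7c:

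- that the 95% intervals for Outcomes 1-6 use site-level cluster-robust variance (sandwich or survey-linearised), or a bootstrap that resamples whole sites;
- the population to which each interval refers: the patients of the clinics captured, the national ART cohort, or a wider population;
- that where the data fully enumerate that population, the value is reported without a sampling interval.

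No regression model is needed, so the descriptive intent is kept. The cost is a few sentences and a cluster or survey option in the software, with site already the planned clustering unit for Outcomes 9-11. The downside is wider intervals, most visibly for SOP agreement and for clinic-level contrasts.
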